7.7. Removal of Subjects from Therapy or Assessment

A subject is free to withdraw his/her consent and discontinue participation in the study at any time for any reason. A subject's participation must therefore be terminated immediately upon his/her request, and the reason(s) for discontinuation appropriately documented.

A subject must be discontinued from the study, including the Titration, Double-Blind Phases, and Open-Label Safety Extension Phase, for any of the following reasons:

- Safety reasons, including AEs or significant concomitant illness, injury or urgent surgeries/procedures that would, in the judgment of the investigator, affect assessments of clinical status to a significant extent, require discontinuation of study drug, or both
 - Every attempt should be made to collect samples for a urine toxicology test and BPN blood concentration if a subject experiences a SAE or is discontinued from the study due to an AE. The investigator will remain blinded to the results until the study blind is broken.

- At the request of the Sponsor, regulatory agency, or Institutional Review Board (IRB)
- Subject is lost to follow-up
- Subject treatment allocation is unblinded
- Death of subject

A subject may also be discontinued from the study, at the discretion of the investigator and/or Sponsor, for any of the following reasons:

- Lack of efficacy
- Subject refuses or is unable to adhere to the study protocol visits and procedure
- Major protocol violation
- Pregnancy
- Use of unacceptable concomitant medication(s)
- It is not considered in the best interest of the subject to continue
- Administrative reasons (e.g., termination of enrollment or study)

The investigator must maintain a record of all subjects who discontinue from the study prior to completion. The reason(s) for study discontinuation will be documented. In the event that a subject chooses to withdraw from the study, the Investigator should make a reasonable attempt to obtain and record the reason(s) for withdrawal in as much detail as possible, although the subject is not obligated to provide such reason(s).

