In the event that a subject is discontinued while at the clinical site, the early termination procedures shown in the Schedule of Assessments ([Table 6](#), [Table 7](#), [Table 8](#), and [Table 10](#)) should be performed prior to discharge from the clinical site. For any case of early discontinuation, whether or not the subject is at the clinical site, the investigator should ask the subject to return for the early termination procedures, provided that the subject has not withdrawn consent for those procedures. If the subject has not withdrawn consent for procedures, the sponsor can hire a third-party vendor to locate the subject so that the early termination procedures can be performed. If subject refuses to complete early termination procedures, this information will be recorded.

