8.3. Method of Assigning Subjects to Treatment Groups

Randomization will be used to avoid bias in the assignment of subjects to treatments, to increase the likelihood that known and unknown subject attributes (e.g., demographics, baseline characteristics) are evenly balanced across treatment groups, and to enhance the validity of statistical comparisons across

treatment groups.

Subjects who provide written informed consent will be assigned a unique number in the screening process. This number will be used to identify the subject throughout the study.

Subjects who meet the eligibility criteria will be randomized in a 1:1 ratio (Group 1: active CAM2038 SC injections or Group 2: placebo SC injections). Randomization will be stratified based on double blind dosing regimen. Subjects randomized at a titration dose of either 4, 8 or 12 mg will remain on weekly doses. Subjects randomized at a titration dose of 16, 24, or 32 mg will transition to monthly dosing.

Therefore, there will be four different dose types.

- A1 – Active weekly
- B1 – Placebo weekly
- A4 – Active monthly
- B4 – placebo monthly

Due to the size of the study, it is expected that subjects will be balanced for various other baseline factors, including age.

Once any subject number or randomization number is assigned, it cannot be reassigned to any other subject. This study will use central randomization, as described in Section 9.2.

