11.4. Determination of Sample Size

It is estimated that 170 subjects per treatment group will provide 90% power with a 2-sided test at a 5% significance level and standard deviation of API at Week 12 of 2.0 to detect a treatment effect of 0.7 unit (or a standardized effect of 0.35) in change from baseline in the WAAP scores at Week 12 (Double-Blind Phase). Considering a titration success rate of 60%, this study will enroll approximately 875 subjects to obtain 340 subjects achieving a successful dose in order to be randomly assigned to study drug treatment in the Double-Blind Phase.

Additional statistical details will be outlined in the SAP.

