9.3 PRIMARY ANALYSIS

The primary analysis will be performed based on the mITT Population.

WAAPI over time will be performed by longitudinal data analysis using mixed-model repeated measures (MMRM) methods. All post-randomization baseline observations will be utilized; missing values will remain as missing (i.e. no attempt will be made to impute missing values, and only observed values will be used in the data analysis). The model will include treatment, post-baseline weeks, treatment by week interaction as fixed effects, and baseline WAAPI as the covariate. The covariance will assume to be unstructured. If the estimates do not converge, SAS default covariance structure (variance components) will be assumed. The MMRM with maximum likelihood estimation will utilize the following pseudo-SAS code for analysis:

```
proc mixed data = WAAPI Data method = ml;
class treatment week subject;
model Change in WAAPI = treatment week treatment*week baseline;
repeated week / subject = subject type = un;
lsmeans treatment / pdiff cl e;
lsmeans treatment*week /slice = week cl diff;
ods output diffs = alldiff;
```

If the estimation under type=un cannot converge, the SAS default (variance components) will be used. The estimated treatment effects, treatment differences, and the two-sided 95% confidence intervals of the treatment differences at all post-baseline timepoints will be presented. The primary comparison will be the treatment difference at Week 12.

A clear advantage of using MMRM is that this method does not require artificial missing imputations that would often create biases. The MMRM method is valid if the “missing at random” assumption holds. The trial is designed to minimize missing values: (a) Subjects who discontinue taking study medication are permitted to remain in the study, and safety and efficacy data will continue to be collected from these subjects; (b) Liberal use of rescue medication is allowed during the study, and data collection will continue even after subjects take these medications, and (c) Robust efficacy data collection procedures will be used in the trial.

Using the procedures above, it is expected that missing values will be minimal and that “missing at random” is a reasonable assumption. Therefore, the “MMRM without missing” imputation is reasonable. Sensitivity analyses of missing value imputations will be performed to support the robustness of the conclusion (see [Section 9.4](#)).

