9.4 SENSITIVITY ANALYSES

Missing values sensitivity analyses:

As the MMRM analysis does not impute missing values, sensitivity analyses with various missing value imputation methods will be performed. Sensitivity analyses based on the random replace and tipping point methods will be performed to assess the robustness of the primary efficacy data.

If all daily ratings are missing for a given week, the missing change from baseline values at a given week will be imputed using the following methods.

Random replacement method

Missing change from baseline in WAAPI at Week J will be imputed with randomly generated values from a normal distribution using a seed of 153928221. The normal distribution will be assumed to have a mean x and a standard deviation of y , where x and y are the mean and standard deviation of the changes at Week J based on all subjects (i.e., subjects from both treatment groups) with non-missing values. It should be noted that, if treatment is effective, the results of this missing value imputation method will be more conservative (i.e., biased in favor of the control).

Tipping point method

Missing change values at Week J from placebo subjects will be imputed with the value that is equal to the mean changes among placebo subjects at that week. Missing change values from active treatment subjects will be imputed with the value that is $k\%$ worse than the mean WAAPI from the placebo group at that week, where $k=0, 5, 10, 20, 30, 40 \dots 100$, until tipping (i.e., the treatment difference at Week 12 is no longer significant at a two-sided significance level of 0.05).

Additional Sensitivity Analyses:

Inclusion of paper diary data from the primary analysis

The primary efficacy variable will be analyzed including available paper diary data collected.

Exclusion of weekly average diary entries that do not have at least 5 daily entries during randomization baseline week (Week -1) and at the end of treatment (Week 12)

The primary efficacy variable will be analyzed after treating WAAPI for any giving week as missing if average pain scores are available for less than 5 days in that week.)

Exclusion of subjects who do not complete at least 4 weeks of treatment

The primary efficacy variable will be analyzed in subjects who participate in the study for at least 4 weeks of the double-blind period.

Exclusion of subjects who do not complete at least 8 weeks of treatment

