9.9 POWER AND SAMPLE SIZE JUSTIFICATION

A sample size of 170 subjects per treatment group will provide over 90% power to detect a treatment difference at a two-sided 5% significance level. In the sample size calculation, a treatment difference of 0.7 units and an SD of 2 (or a standardized effect of 0.35) for the primary efficacy variable were assumed.

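### SAP 9.3 supports missing-at-random partly by off-drug follow-up that the protocol does not generally provide, and the planned k = 0 tipping-point step barely tests what follows from that.

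*SAP*

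**What the plan says.** SAP 9.3 fits an MMRM to observed weekly change in WAAPI without imputation and notes that it is valid under missing-at-random. Three design features are offered in support. The first is "Subjects who discontinue taking study medication are permitted to remain in the study", with safety and efficacy data still collected. The SAP concludes that few values will be missing.

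Protocol 7.7 opens its mandatory list with "A subject must be discontinued from the study, including the Titration, Double-Blind Phases, and Open-Label Safety Extension Phase". That list includes safety reasons that require study drug to be stopped. Lack of efficacy is on a second list, at the discretion of the investigator or sponsor, but it too is an exit from the study. For any early discontinuation, "the investigator should ask the subject to return for the early termination procedures". Protocol 8.1.4 returns subjects at early termination to standard care or their earlier treatment. The same section says that a subject who withdraws after needing rescue above the maximum should have assessments completed for the remaining visits.

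SAP 9.4 plans random replacement from the pooled mean and SD of both arms, and a tipping-point analysis. In the latter, missing placebo values take the placebo mean, and missing active values are set by reference to the placebo mean with a penalty of k%. Separate reruns include "Exclusion of subjects who do not complete at least 4 weeks of treatment" and the same at 8 weeks.

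**The concern.** The justification for the primary model describes a trial in which stopping injections and leaving the study are separate events. Protocol 7.7 mostly treats them as one. If diary scores end at the drug stop, the MMRM projects an active dropout from that subject's own earlier scores and the active-arm trajectory. In a randomised-withdrawal trial this amounts to assuming that benefit largely continues after the drug has stopped. If the effect of interest counts pain after stopping, the estimate can be too large. What carries the conclusion is then the sensitivity analysis, so it matters whether that analysis really tests the point.

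**Working it through.** **1. The plan's own figure.** Protocol 11.4: "It is estimated that 170 subjects per treatment group will provide 90% power with a 2-sided test at a 5% significance level", with "standard deviation of API at Week 12 of 2.0 to detect a treatment effect of 0.7 unit". SAP 9.9: "A sample size of 170 subjects per treatment group will provide over 90% power". Allocation is equal (protocol 8.3: "Subjects who meet the eligibility criteria will be randomized in a 1:1 ratio").

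- SE = 2 × √(2/170) = 0.217
- z = 0.7/0.217 = 3.23
- Power = Φ(3.23 − 1.96) = 89.7%; 90% power needs 172 per arm

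The stated figure reproduces to rounding.

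**2. What happens to scores after drug stop.**

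| Route | Protocol | Data afterwards |
|---|---|---|
| Safety reason requiring drug stop | 7.7, mandatory study exit | Early-termination procedures |
| Lack of efficacy | 7.7, discretionary study exit | Early-termination procedures |
| Withdrawal over the rescue maximum | 8.1.4, subject's choice | Assessments at remaining visits |

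Only the third route matches the SAP's statement.

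**3. Size if no scores follow.** Assume that a share f of the active arm is unobserved at Week 12 and has placebo-like pain. The difference counting off-drug outcomes is 0.7 × (1 − f). Neither document gives a double-blind dropout rate, so f is an assumed range.

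| f | 0.7 × (1 − f) | 0.7 relative to it |
|---|---|---|
| 20% | 0.56 | 25% larger |
| 30% | 0.49 | 43% larger |
| 40% | 0.42 | 67% larger |

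A simulation checked this: 170 per arm, six post-baseline time points, SD 2, correlation 0.7, maximum likelihood with unstructured covariance, equal dropout unrelated to the scores, 1,500 replicates. At 20%, 30% and 40% dropout the MMRM averaged 0.707, 0.704 and 0.699. The differences counting off-drug outcomes were 0.567, 0.495 and 0.419. The k = 0 step gave 0.563, 0.491 and 0.419, so its point estimate is right under this assumption.

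**4. Does k = 0 test significance?** Read k = 0 as the placebo mean change. Use a Week 12 two-sample comparison, which simplifies the MMRM, with share p = 1 − f observed in each arm.

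- Observed subjects only: z = 0.7 / (2√(2/(170p))) = √p × 3.23.
- k = 0: the effect is 0.7p. The constants add almost no variance, so SE ≈ √p × 0.217 and again z ≈ √p × 3.23.

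Effect and SE shrink together and z hardly moves. In full at p = 0.7, the spread between observed and imputed active subjects adds 0.7² × 0.7 × 0.3 = 0.103 to the active-arm variance:

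- Observed only: SE = 2√(2/119) = 0.259; z = 2.70; 77% significant.
- k = 0: SE = √((0.7 × 4 + 0.103 + 0.7 × 4)/170) = 0.183; z = 0.49/0.183 = 2.68; 76% significant.
- Placebo-like outcomes actually observed: SE = √((4 + 0.103 + 4)/170) = 0.218; z = 0.49/0.218 = 2.24; 61% significant.

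With 30% of values missing, the k = 0 standard error is smaller than with none missing (0.183 against 0.217). Simulation of the same comparison gave the same shares.

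**5. Larger k.** SAP 9.4 replaces missing changes with a value k% worse than the placebo mean WAAPI. WAAPI is a level on which higher is worse, while SAP 9.2 defines change so that positive means improvement. The two scales are not interchangeable. If the mean change m is meant instead, the penalty is k/100 × |m|, which vanishes when m is near zero.

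**The case against.** The strongest reply is that the plan already contains this scenario: placebo-level imputation for missing active values is the k = 0 step, and larger k is meant to go further. That stands for the point estimate. A reader might infer that the plan has no analysis of lost benefit, and SAP 9.4 contradicts that. The reply fails on significance, for the reason in steps 4 and 5. Random replacement does not fill the gap, since a pooled mean leaves active dropouts part of the benefit. The 4- and 8-week reruns select on post-randomisation participation. SAP 9.4 lists them apart from the missing-value analyses and does not present them as a test of missing-at-random.

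A reader might also infer that the protocol removes everyone who stops drug. It does not say so. Exit for lack of efficacy is discretionary, and 8.1.4 asks for remaining-visit assessments on one route, perhaps a common one on placebo, since 8.1.5 expects more pain and rescue use there. Section 9.5 lets injections be discontinued without mentioning study exit, and 9.5.11 links a withheld dose to study discontinuation only in some cases. Tables 6 and 7 schedule the diary by study week, with no stated link to dosing. The protocol is therefore inconsistent with itself as well as with the SAP.

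The size is open to challenge too. The MMRM conditions on each subject's own scores, so someone leaving in worsening pain is not simply given a completer's result, and any off-drug scores collected would enter the model. Full reversion by Week 12 is not assured: protocol 8.7 describes receptor dissociation lasting up to 2 weeks (weekly product) or at least 2 months (monthly product), and leavers move to other treatment.

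**Conclusion.** The point holds as a documentary conflict with a real analytic consequence. The first support that SAP 9.3 offers for missing-at-random is not backed by protocol 7.7, and the expectation of few missing values loses that support. The 0.56, 0.49 and 0.42 are conditional illustrations. They assume 20%, 30% or 40% active dropout, no scores after the drug stop, and placebo-like pain by Week 12. It is tempting to read them as a known 25% to 67% inflation of the primary result. The documents do not support that, because no dropout rate is given and the net bias also depends on placebo dropouts and on treatment after exit. The weakness of the k = 0 step follows from the arithmetic within the two-sample simplification with equal dropout. The primary MMRM can stay, but its supporting analysis should be strengthened.

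**What to change.** 1. Reconcile protocol 7.7 and 8.1.4 with SAP 9.3 on whether diary scores are collected after injections stop, by route of discontinuation. This concerns data collection only; which subjects should stop treatment is not at issue. If scores are not generally collected, remove or qualify the first support in SAP 9.3 and the conclusion about few missing values.

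2. Pre-specify control-based (placebo-reference) multiple imputation as the main supporting analysis. Name the variance method, for example Rubin's rules, so that missing data do not add apparent precision. This has to be explicit, because the repeated-sampling SE of a placebo-reference estimate also shrinks (0.7 × 0.259 = 0.181 in step 4).

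3. Run the tipping point by multiple imputation, with the penalty in points on the change scale. Do not present the 4- and 8-week reruns as evidence about missing data.

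The cost is SAP wording, a little more analysis work, and a protocol clarification if the reconciliation calls for one. The supporting estimate will be somewhat smaller and less precise. The SAP changes should be made before unblinding.

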9.4 SENSITIVITY ANALYSES

Missing values sensitivity analyses:

As the MMRM analysis does not impute missing values, sensitivity analyses with various missing value imputation methods will be performed. Sensitivity analyses based on the random replace and tipping point methods will be performed to assess the robustness of the primary efficacy data.

If all daily ratings are missing for a given week, the missing change from baseline values at a given week will be imputed using the following methods.

Random replacement method

Missing change from baseline in WAAPI at Week J will be imputed with randomly generated values from a normal distribution using a seed of 153928221. The normal distribution will be assumed to have a mean x and a standard deviation of y , where x and y are the mean and standard deviation of the changes at Week J based on all subjects (i.e., subjects from both treatment groups) with non-missing values. It should be noted that, if treatment is effective, the results of this missing value imputation method will be more conservative (i.e., biased in favor of the control).

Tipping point method

Missing change values at Week J from placebo subjects will be imputed with the value that is equal to the mean changes among placebo subjects at that week. Missing change values from active treatment subjects will be imputed with the value that is $k\%$ worse than the mean WAAPI from the placebo group at that week, where $k=0, 5, 10, 20, 30, 40 \dots 100$, until tipping (i.e., the treatment difference at Week 12 is no longer significant at a two-sided significance level of 0.05).

Additional Sensitivity Analyses:

Inclusion of paper diary data from the primary analysis

The primary efficacy variable will be analyzed including available paper diary data collected.

Exclusion of weekly average diary entries that do not have at least 5 daily entries during randomization baseline week (Week -1) and at the end of treatment (Week 12)

The primary efficacy variable will be analyzed after treating WAAPI for any giving week as missing if average pain scores are available for less than 5 days in that week.)

Exclusion of subjects who do not complete at least 4 weeks of treatment

The primary efficacy variable will be analyzed in subjects who participate in the study for at least 4 weeks of the double-blind period.

Exclusion of subjects who do not complete at least 8 weeks of treatment

The primary efficacy variable will be analyzed in subjects who participate in the study for at least 8 weeks of the double-blind period.

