6. GENERAL CONVENTIONS

Unless otherwise stated, all analyses will be performed using SAS Version 9.2, and all hypothesis tests will be conducted at a two-sided significance level of 0.05. P-values will be presented with 3 decimal places, and p-values that are less than 0.001 will be presented as <0.001.

Continuous (non-survival-related) data will be summarized using descriptive statistics: number of observations (n), mean, standard deviation (SD), median, minimum and maximum. Frequencies and percentages will be used to summarize categorical (discrete) data. Presentations of categorical data will generally suppress percentages for items where the count is zero, in order to draw attention to the nonzero counts. In general, mean, SD, median, minimum, maximum and percentages will be presented with one decimal place.

Unless otherwise stated, confidence intervals, when presented, will be constructed at the two-sided 95% level. For binomial variables, the 95% confidence intervals will be constructed using the normal approximation without continuity correction.

Data listings will present all data collected on Case Report Forms (CRFs) by study drug, center and subject number. Unless otherwise stated, data will be presented by treatment and overall.

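### The random-replacement check in SAP 9.4 draws each missing value once, so its verdict depends partly on the seed; many draws from the same distribution would remove this

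*SAP*

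**What the plan says.** SAP 9.4 names two missing-data checks and gives their purpose: "Sensitivity analyses based on the random replace and tipping point methods will be performed to assess the robustness of the primary efficacy data". A week is imputed only under the condition "If all daily ratings are missing for a given week". Under random replacement, each such weekly change is "imputed with randomly generated values from a normal distribution using a seed of 153928221", where "x and y are the mean and standard deviation of the changes at Week J based on all subjects" with data at that week, both arms together. The SAP notes that, if the treatment works, the result is "biased in favor of the control".

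The section gives no number of imputations, no rule for combining results and no repetition over seeds. It does not say which model is fitted to the completed data. The companion tipping-point analysis fills in fixed, mean-based values and uses no random draw. The primary analysis (SAP 9.3) is an MMRM on observed values, and that section expects few missing values without giving a rate.

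**The concern.** One seed and no stated number of imputations amount, as written, to one completed data set. The single draw is an inference from what is absent, because a multiple-imputation procedure also starts from one seed. If multiple imputation was meant, the SAP has to say so.

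Read as it stands, the estimated Week 12 difference from this check contains noise that comes from the random number generator and not from the subjects. Two statisticians who apply the same method to the same trial data with different seeds could report opposite verdicts on robustness. SAP 9.3 relies on the analyses in 9.4 to support the missing-at-random assumption, so the check should not turn on one draw more than it has to.

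**Working it through.** **Inputs.** SAP 9.9: 170 per arm, difference 0.7, SD 2. SAP 6: "all hypothesis tests will be conducted at a two-sided significance level of 0.05". SAP 4.4: 1:1 allocation. The missing rate m at Week 12 is an assumption: 5% to 40%, equal in both arms and unrelated to outcome. The completed data are compared by a two-sample t-test at Week 12, which stands in for the model the SAP does not name.

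**Step 1, the plan's own figure.** SAP 9.9 states: "A sample size of 170 subjects per treatment group will provide over 90% power to detect a treatment difference". The SE of the difference is 2 × √(2/170) = 0.217, and 0.7/0.217 = 3.23. Power is Φ(3.23 − 1.96) = 89.7% (89.6% with the t distribution), and 90% needs 172 per arm. This reproduces the 90% of Protocol 11.4 and falls just short of the SAP's wording.

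**Step 2, noise from the draw alone.** The pooled SD y includes half the arm difference: y² = 2² + 0.35² = 4.12. Each arm has m × 170 drawn values, so the draw adds to the difference an SD of √(2·m·y²/170). At m = 20% this is √(2 × 0.2 × 4.12/170) = 0.098. The expected difference shrinks to (1 − m) × 0.7. The completed-data SE is 0.217 to 0.219 throughout, and dividing the draw SD by it gives the seed-to-seed SD of z.

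**Step 3, how often seeds disagree.** For each m, 1,500 trials were simulated at the design effect. Each was imputed 200 times, and pairs of draws were compared on two-sided p < 0.05 in favour of active.

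| Missing | Expected difference | SD from draw | SD in z | Opposite verdicts, seed pairs |
|---|---|---|---|---|
| 5% | 0.665 | 0.049 | 0.23 | 5% |
| 10% | 0.63 | 0.070 | 0.32 | 9% |
| 20% | 0.56 | 0.098 | 0.45 | 17% |
| 30% | 0.49 | 0.121 | 0.55 | 25% |
| 40% | 0.42 | 0.139 | 0.64 | 30% |

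The last column averages over trials whose observed difference varies around 0.7, so it includes borderline results.

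**Step 4, one fixed trial, 5,000 draws.** Share of draws that are significant, by observed difference:

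| Missing | 0.7 | 0.6 | 0.5 |
|---|---|---|---|
| 10% | 99.7% | 94.8% | 63.6% |
| 20% | 90.4% | 70.5% | 39.4% |
| 30% | 69.8% | 46.8% | 25.0% |

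At an observed 0.7 with 20% missing, the complete-case p is 0.004, while the central 95% range of p over draws is 0.0005 to 0.097. At 30% missing the range is 0.0008 to 0.24.

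**Step 5, is the single-draw test valid?** With equal missingness the shared mean x cancels. Taking y ≈ 2, the variance of the difference is (1 − m)(2·2²/170) + m(2·2²/170) = 2·2²/170, an SD of 0.217, which is what the completed-data test assumes. Simulated type I error was 4.7% to 5.4% at 10% to 40% missing.

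**Step 6, many draws.** Averaging removes the second term of that sum. At 20% missing the true SD falls to √(0.8 × 0.0471) = 0.194 (0.196 by simulation). Rubin's SE is about √(0.218² + 0.098²) = 0.239. In the fixed trial with an observed 0.7, the combined p is 0.019 at 20% missing and 0.048 at 30%.

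**The case against.** The seed is fixed in advance, which makes the result reproducible and rules out choosing a favourable seed. This is one supportive check beside a tipping-point analysis without random draws and four further sensitivity analyses. The MMRM imputes nothing. If missing values are as few as SAP 9.3 expects, the seed hardly matters. All of this stands, but fixing the seed settles which draw is used and does not reduce the dependence on it. The documents also foresee withdrawal: Protocol 8.1.5 expects pain to rise on placebo, and SAP 9.4 excludes early leavers in two analyses.

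A reader might infer more, and the documents do not support it:

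- **That the check is invalid and says nothing about the primary result.** Step 5 shows that it keeps its level under equal missingness. Nor does a single-draw SE below Rubin's SE (0.218 against 0.239 at 20%) show that it is too small, since for this pooled imputation Rubin's is the one that overshoots.
- **That independent weekly draws damage the covariance in the MMRM.** SAP 9.4 does not name the model for the imputed data, and the calculations here use Week 12 only, so no such effect has been shown.
- **That the draws should use arm, baseline and earlier weeks.** That is a missing-at-random model, the assumption the MMRM already makes, and it would largely repeat the primary analysis. The pooled distribution departs from it deliberately, against the treatment.

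**Conclusion.** The point holds as a cheap improvement. Followed as written, the random-replacement result carries avoidable noise of about 0.05 to 0.14 NRS points in the Week 12 difference for 5% to 40% missing. The seed has little influence at 5% to 10% missing with an observed difference near 0.7. It has a clear influence at 20% or more, or at lower rates when the result is borderline: at 10% missing and an observed 0.5, only 64% of draws are significant. What is lost is precision and stability of a supportive check, not its validity, and the primary analysis is untouched.

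The sizes rest on the planning SD and sample size, equal missingness unrelated to outcome, and a Week 12 t-test in place of a longitudinal model. The mITT Population leaves out two sites, so if the analysed arms are smaller than 170 the noise is larger, in proportion to 1/√n.

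**What to change.** Amend SAP 9.4 as follows:

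- Keep the pooled Week J distribution and the stated seed, and generate at least 100 imputed data sets.
- Analyse each with the primary model of SAP 9.3 and combine by Rubin's rules.
- Report the spread of the Week 12 difference and p-value over the draws beside the combined result.

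The change can go in as a numbered revision under SAP 6.2 before unblinding. It costs a short paragraph and standard programming.

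The downside is that Rubin's SE is conservative for this imputation (about 0.24 against a true SD of about 0.20 at 20% missing), so the check becomes harder to pass. In the simulation at the design effect, with 50 imputations, the chance of a significant result went from 83% to 82% at 10% missing, 74% to 68% at 20%, and 60% to 48% at 30%. The spread over draws lets a reader see how much of a non-significant result is due to this.
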